8.2.5. Days of Non-Invasive Ventilation/High-Flow Oxygen

Duration of non-invasive ventilation/high flow oxygen days will be summarized in a table using medians and quartiles by treatment arm. This will only include subjects in category 6 or 7 at enrollment. Analyses will be performed in the ITT population, Treated population, and a subset of the Treated population of treated subjects only as subjects who are not treated are terminated from the study immediately and are included in the ITT/Treated analyses with a count of 1 day. Bee swarm plots of non-invasive ventilation/high flow oxygen days by treatment arm will be generated, where subject whose days are imputed to the maximum of 28 days due to death are grouped separately from subjects who do not die.

8.2.6. Incidence of New Non-Invasive Ventilation/High-Flow Oxygen

The incidence and duration of new Non-Invasive Ventilation/High-Flow Oxygen use will be analyzed by treatment arm. This will only include subjects in category 4 or 5 at enrollment. The incidence of new oxygen use will be analyzed by treatment arm. This will only include subjects in category 4 at enrollment. New use will be identified by a post-enrollment score of at least 6. The number of subjects reporting new use and the incidence rate (and CI) will be reported.

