3.3.6. Days of Non-invasive ventilation/high-flow oxygen

Non-invasive ventilation/high flow-oxygen days will be defined as the number of days where the clinical status score is equal to 6. After discharge, the CRF question regarding days of ventilation will be used. The total number of days will be the sum of all reported days, regardless of whether the days occur consecutively or in disjoint intervals. See Section 6.5 for the plan for handling subjects who do not have data through Day 29 or die prior to Day 29.

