3.3.7. Days of Ventilation/ECMO

Ventilator / ECMO days will be defined as the number of days where the clinical status score is equal to 7. After discharge, the CRF question regarding days of ventilation will be used. The total number of days will be the sum of all reported days, regardless of whether the days occur consecutively or in disjoint intervals. See Section 6.5 for the plan for handling subjects who do not have data through Day 29 or die prior to Day 29.

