3.3.8. Days of Oxygen

Oxygen days will be defined as the number of days where the clinical status score is equal to 5, 6, or 7. After discharge, the CRF question regarding days of oxygenation will be used. The total number of days will be the sum of all reported days, regardless of whether the days occur consecutively or in disjoint intervals. See Section 6.5 for the plan for handling subjects who do not have data through Day 29 or die prior to Day 29.

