4.3. Efficacy and Safety Variables

For each study day while the patient is hospitalized, the clinical status will be recorded on an 8-point ordinal scale as follows:

- Day 1 – The clinical assessment at the time of randomization.
- Day 2 - The most severe assessment occurring at any time between randomization and midnight the day of randomization.
- Day 3+ - The most severe assessment occurring from midnight to midnight (00:00 to 23:59) of the prior day (e.g., the value recorded on Day 3 will be the most severe outcome that occurred on Day 2).

where the clinical status scale is defined as follows:

8. Death;
7. Hospitalized, on invasive mechanical ventilation or ECMO;
6. Hospitalized, on non-invasive ventilation or high flow oxygen devices;
5. Hospitalized, requiring supplemental oxygen;
4. Hospitalized, not requiring supplemental oxygen- requiring ongoing medical care (COVID-19 related or otherwise);
3. Hospitalized, not requiring supplemental oxygen - no longer requires ongoing medical care;

2. Not hospitalized, limitation on activities;
1. Not hospitalized, no limitations on activities

A modified version of the ordinal scale will be used in sensitivity analyses of the primary and secondary outcomes. The modified scale will be as follows:

8. Death;
7. Hospitalized, on invasive mechanical ventilation or ECMO;
6. Hospitalized, on non-invasive ventilation or high flow oxygen devices;
5. Hospitalized, requiring supplemental oxygen;
4. Hospitalized, not requiring supplemental oxygen- requiring ongoing medical care (COVID-19 related or otherwise);
3. Not hospitalized, limitation on activities;
2. Hospitalized, not requiring supplemental oxygen - no longer requires ongoing medical care; or Not hospitalized, no limitations on activities.

That is, category 1 and 3 of the original scale will be combined into the lowest category.

NEWS has demonstrated an ability to discriminate subjects at risk of poor outcomes. This score is based on 7 clinical parameters (see [Table 1](#)). This should be evaluated at the first assessment of a given study day and prior to administration of study product. The 7 parameters can be obtained from the hospital chart using the last measurement prior to the time of assessment and a numeric score given for each parameter (e.g., a RR of 9 is one point, oxygen saturation of 92 is two points). This is recorded for the day obtained. i.e., on Day N, the Day N score is obtained and recorded as the Day N score.

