8.2.4. Incidence of New Oxygen use

The incidence and duration of new oxygen use will be analyzed by treatment arm. This will only include subjects in category 4 at enrollment. New use will be identified by a post-enrollment score of at least 5; the number of subjects reporting new use and the incidence rate (and CI) will be reported.

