8.2.8. Incidence of New Non-Invasive Ventilation/High-Flow Oxygen

The incidence and duration of new Non-Invasive Ventilation/High-Flow Oxygen use will be analyzed by treatment arm. This will only include subjects in category 4, 5, or 6 at enrollment. The incidence of new oxygen use will be analyzed by treatment arm. This will only include

subjects in category 4 at enrollment. New use will be identified by a post-enrollment score of 7. The number of subjects reporting new use and the incidence rate (and CI) will be reported.

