Table 28: Time to Improvement on the 8-Point Ordinal Scale by Treatment Group – Remdesivir Retreatment Sensitivity Analysis on Subjects with Clinical Status Score of 7 at Enrollment

Table 29: Time to Improvement by at least Two Clinical Status Categories on the 8-Point Ordinal Scale by Treatment Group: Alternate Ordinal Scale

Table 30: Time to Improvement by at least One Clinical Status Category on the 8-Point Ordinal Scale by Treatment Group within Subgroups – ITT Population

Table 31: Time to Improvement by at least One Clinical Status Category on the 8-Point Ordinal Scale by Treatment Group within Subgroups – Treated Population

Table 32: Time to Improvement by at least Two Clinical Status Categories on the 8-Point Ordinal Scale by Treatment Group within Subgroups – ITT Population

Table 33: Time to Improvement by at least Two Clinical Status Categories on the 8-Point Ordinal Scale by Treatment Group within Subgroups – Treated Population

Programming notes for Tables 30 – 33:

Instead of the “Analysis Population” column, a column titled “Grouping Variable” will be to the left of Treatment Group. Rows will be generated for each subgroup.

Table 34: Clinical Status Scores by Treatment Group and Study Visit – ITT Population

Study Visit	Ordinal Scale Measure	Remdesivir (N=X)			Placebo (N=X)			All Subjects (N=X)		
		n	%	95% CI	n	%	95% CI	n	%	95% CI
Day 1	Death at or before Study Visit (8)	x	x	x.x, x.x	x	x	x.x, x.x	x	x	x.x, x.x
	Hospitalized, on invasive mechanical ventilation or ECMO (7)	x	x	x.x, x.x	x	x	x.x, x.x	x	x	x.x, x.x
	Hospitalized, on non-invasive ventilation or high flow oxygen devices (6)	x	x	x.x, x.x	x	x	x.x, x.x	x	x	x.x, x.x
	Hospitalized, requiring supplemental oxygen (5)	x	x	x.x, x.x	x	x	x.x, x.x	x	x	x.x, x.x
	Hospitalized, not requiring supplemental oxygen - requiring ongoing medical care (COVID-19 related or otherwise) (4)	x	x	x.x, x.x	x	x	x.x, x.x	x	x	x.x, x.x
	Hospitalized, not requiring supplemental oxygen - no longer requires ongoing medical care (3)	x	x	x.x, x.x	x	x	x.x, x.x	x	x	x.x, x.x
	Not hospitalized, limitation on activities and/or requiring home oxygen (2)	x	x	x.x, x.x	x	x	x.x, x.x	x	x	x.x, x.x
	Not hospitalized, no limitations on activities (1)	x	x	x.x, x.x	x	x	x.x, x.x	x	x	x.x, x.x
	No clinical status score reported – Hospitalized subjects	x	x	x.x, x.x	x	x	x.x, x.x	x	x	x.x, x.x
	No clinical status score reported – Discharged subjects	x	x	x.x, x.x	x	x	x.x, x.x	x	x	x.x, x.x

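### SAP 8.2.4 and 8.2.6 let a death alone count as new respiratory support, 8.2.6 does not match its own day count, and the 1-day count for untreated subjects is unreconciled with 6.5 (minor; other secondary summaries only)

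*SAP*

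**What the plan says.** **Scale and recording.** SAP 3.2 and 4.3 code death as 8, invasive ventilation or ECMO as 7, non-invasive ventilation or high-flow oxygen as 6, and supplemental oxygen as 5. From Day 3 the recorded score is "The most severe assessment occurring from midnight to midnight (00:00 to 23:59) of the prior day". In the Table 34 shell, the score-8 row takes in anyone who died at or before the visit.

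**New-use incidence.**
- 8.2.4, oxygen, at risk category 4: "New use will be identified by a post-enrollment score of at least 5".
- 8.2.6, non-invasive or high-flow, at risk category 4 or 5: "New use will be identified by a post-enrollment score of at least 6".
- 8.2.8, at risk category 4, 5 or 6: "New use will be identified by a post-enrollment score of 7".

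**Day counts.**
- 3.3.8: "Oxygen days will be defined as the number of days where the clinical status score is equal to 5, 6, or 7".
- 3.3.6, non-invasive days: "number of days where the clinical status score is equal to 6".
- 3.3.7, ventilator/ECMO days: "number of days where the clinical status score is equal to 7".

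All three send subjects who die, or who lack data through Day 29, to 6.5. Section 6.5 treats an early terminator last seen on a given support as staying on it through Day 29. It states a 28-day value for death only under hospitalization. Sections 8.2.3, 8.2.5 and 8.2.7 nevertheless describe plots in which deaths have had their support days set to a 28-day maximum. The same three sections say that untreated subjects leave the study at once and enter with 1 day.

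**The concern.** The new-use endpoints are meant to show how many subjects came to need a given level of support. Two of the three parallel rules have no upper limit and so take in death, while the third does not. A death without support is then a new user in two tables and a non-event in the third.

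In 8.2.6, incidence and duration also describe different subjects. The section promises both, but the event set is wider than the score that defines the days.

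The 1-day count raises a separate problem. Two programmers working from this SAP could give the same untreated subject different values, depending on whether they follow Section 8.2 or Section 6.5.

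**Working it through.** No plan figure needs reproducing here. The check is an enumeration of the rules.

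**(a) Event scores against day-count scores**

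| Section | Event scores | Day-count scores | In event set only |
|---|---|---|---|
| 8.2.4 oxygen | 5, 6, 7, 8 | 5, 6, 7 (3.3.8) | 8 |
| 8.2.6 non-invasive/high-flow | 6, 7, 8 | 6 (3.3.6) | 7, 8 |
| 8.2.8 | 7 | 7 (3.3.7) | none |

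Three subjects show what follows:

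1. Baseline 4, discharged, dies after discharge with no score of 5 to 7. This is a new user in 8.2.4 and 8.2.6 but not in 8.2.8.
2. Baseline 5, next recorded score 7, never 6. This is a new non-invasive user in 8.2.6 with 0 inpatient non-invasive days under 3.3.6.
3. Baseline 4, worsens and dies within one calendar day. Only score 8 is recorded. The score cannot show whether support was given.

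The table uses 3.3.6 to 3.3.8 alone. If the 28-day death imputation in 8.2.3, 8.2.5 and 8.2.7 also applied to new-use durations, a death would carry support days. Section 6.5 does not say whether it does.

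**Size of (a).** The overstatement in an arm is d/n, where d is the number of deaths with no support and n is the number at risk. The documents give neither. As an illustration, assume that category 4 makes up 15–25% of 572 to 800 subjects. Then n per arm for 8.2.4 runs from 572 × 0.15 / 2 = 42.9 to 800 × 0.25 / 2 = 100. One such death adds 100/42.9 = 2.3 to 100/100 = 1.0 percentage points.

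**(b) Untreated subject with a Day 1 score only, terminated at once**

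| Section | Baseline | Section 8.2 value | Observed days only | Section 6.5 value |
|---|---|---|---|---|
| 8.2.3 | 5, 6 or 7 | 1 | 1 | 28 |
| 8.2.5 | 6 | 1 | 1 | 28 |
| 8.2.5 | 7 | 1 | 0 | 0 |
| 8.2.7 | 7 | 1 | 1 | 28 |

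Counting Day 1 as well as Days 2 to 29 gives 1 + 28 = 29. The table uses 28, the maximum named in Section 8.2. In the third row neither reading gives 1, because the subject has no score of 6.

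**Size of (b).** For 8.2.3 and 8.2.7 in the ITT population, let u be the untreated fraction, assumed to be 1–5%. The ITT median then falls at the (0.50 − u)/(1 − u) quantile of the treated under the 1-day rule, and at 0.50/(1 − u) under 6.5.

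- u = 1%: 0.49/0.99 = 49.5% against 0.50/0.99 = 50.5%.
- u = 5%: 0.45/0.95 = 47.4% against 0.50/0.95 = 52.6%.

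This holds only if the median lies strictly between 1 day and the maximum. With deaths set to 28 days, that may fail in 8.2.7. No such figure is given for 8.2.5, where treated category 7 subjects may also have 0 days.

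**The case against.** **Death in the trigger may be deliberate.** The SAP refers to a 28-day value for deaths in the support-day summaries, so death does enter the duration measures somewhere. On that reading 8.2.8 is the odd one out. This stands as far as it goes: removing score 8 from the triggers without settling the duration rule could leave deaths with 28 support days and no event. It does not defend the present text, because 6.5 states no such rule for support days and the three triggers still disagree.

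**Not every death without a prior support score is a false event.** A reader might infer that all of them are. The documents do not support this. Worst-of-day scoring can hide support given on the day of death, so limiting the trigger to scores 5 to 7 would lose real events. Protocol 8.1.2.1 lists oxygen, non-invasive, high-flow, invasive and ECMO requirements as separate measures, and Protocol 9.2 says the elements of the scale are captured separately. A better source therefore exists.

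**A score of 6 or more may mean this level of support or higher.** That is a legitimate endpoint, but the section is neither labelled nor counted that way.

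**The 1-day rule is specific and reasoned.** Sections 8.2.3, 8.2.5 and 8.2.7 name the untreated subjects, say why they are short of data, and add a treated-only analysis. They can be read as an exception to 6.5. A reader might infer that 28 days is the right value and 1 day is an error throughout. The documents do not support that either: the choice between the two is open, and what is missing is a statement of which governs. The objection fails only for category 7 in 8.2.5.

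**Conclusion.** The point holds as a minor one. As written, score 8 alone triggers new use in 8.2.4 and 8.2.6 but not in 8.2.8. In 8.2.6 a move straight to score 7 counts as non-invasive use, against 3.3.6. The 1-day count is wrong for untreated category 7 subjects in 8.2.5. Elsewhere it is an unreconciled conflict with 6.5, not a demonstrated error.

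The size is not known from the documents. It depends on the number of deaths without support, the number of direct moves to score 7, and the number of untreated subjects, none of which is given. The ranges above rest on assumed shares. A reader might take the 1–3% Day 15 deaths in SAP Table 4 as a ceiling on the death effect. Those values describe the whole control arm, not category 4 or 5, and follow-up runs to Day 29.

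The primary analysis, the key secondary analysis and the sample size are untouched. Hospital days (8.2.9) carry the same 1-day wording, but 6.5 has no rule for subjects terminated while still in hospital, so this conflict does not arise there.

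**What to change.** 1. In 8.2.4, 8.2.6 and 8.2.8, state that score 8 alone does not trigger new use, and report deaths separately in the same way for all three. Where death masks support given the same day, take the event from the separately captured support measures (Protocol 8.1.2.1, 9.2).
2. In 8.2.6, choose one of two consistent definitions. Either the event is score 6, matching 3.3.6, or the event is labelled *non-invasive/high-flow or higher support* and duration is counted at scores 6 and 7.
3. In 6.5, state whether the 28-day death imputation applies to support days, including new-use durations, and use one death rule for incidence and duration.
4. In 8.2.5, set untreated category 7 subjects to 0 non-invasive days. For 8.2.3, 8.2.7 and category 6 in 8.2.5, either apply 6.5 or write the 1-day rule into 6.5 as an explicit exception. Keep the treated-only analysis as the sensitivity analysis.
5. Editorial: retitle 8.2.8 and its first sentence as new invasive ventilation/ECMO, in line with SAP 3.1 and Table 45. Delete the stray sentences on new oxygen use in category 4 from 8.2.6 and 8.2.8. Correct the ITT/Treated wording, since 6.3.1 excludes untreated subjects from the Treated population.

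The cost is SAP wording and programming of tables already planned. No new data are needed.

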8.2.7. Days of Invasive Mechanical Ventilation/ECMO

Duration of invasive Mechanical Ventilation/ECMO days will be summarized in a table using medians and quartiles by treatment arm. This will only include subjects in category 7 at enrollment. Analyses will be performed in the ITT population, Treated population, and a subset of the Treated population of treated subjects only as subjects who are not treated are terminated from the study immediately and are included in the ITT/Treated analyses with a count of 1 day. Bee swarm plots of invasive Mechanical Ventilation/ECMO days, and days hospitalized by treatment arm will be generated, where subject whose days are imputed to the maximum of 28 days due to death are grouped separately from subjects who do not die.

8.2.8. Incidence of New Non-Invasive Ventilation/High-Flow Oxygen

The incidence and duration of new Non-Invasive Ventilation/High-Flow Oxygen use will be analyzed by treatment arm. This will only include subjects in category 4, 5, or 6 at enrollment. The incidence of new oxygen use will be analyzed by treatment arm. This will only include

subjects in category 4 at enrollment. New use will be identified by a post-enrollment score of 7. The number of subjects reporting new use and the incidence rate (and CI) will be reported.

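### SAP 8.2.8 labels new invasive ventilation/ECMO as new non-invasive support, and the population and event wording of 8.2.6 and 8.2.8 needs correcting

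*SAP*

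**What the plan says.** SAP 8.2.6 and 8.2.8 share a heading, on the incidence of new non-invasive ventilation or high-flow oxygen, and an opening sentence. In 8.2.8 that sentence reads "The incidence and duration of new Non-Invasive Ventilation/High-Flow Oxygen use will be analyzed by treatment arm".

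- **8.2.6** gives the population as "This will only include subjects in category 4 or 5 at enrollment". It continues "The incidence of new oxygen use will be analyzed by treatment arm. This will only include subjects in category 4 at enrollment", and the event rule follows at once: "This will only include subjects in category 4 at enrollment. New use will be identified by a post-enrollment score of at least 6".
- **8.2.8** gives the population as "This will only include subjects in category 4, 5, or 6 at enrollment". It then repeats the sentence on new oxygen use in category 4, and the event rule follows directly: "New use will be identified by a post-enrollment score of 7".

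SAP 3.3.6 defines the matching duration: "Non-invasive ventilation/high flow-oxygen days will be defined as the number of days where the clinical status score is equal to 6". SAP 3.3.7 defines ventilator/ECMO days by score 7. SAP 3.1 lists the incidence and duration of new mechanical ventilation or ECMO as an objective in its own right, separate from new non-invasive support.

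**The concern.** An analyst who follows 8.2.8 as titled would report an invasive ventilation/ECMO count as new non-invasive use. The population would include category 6, whose members already receive non-invasive support at enrollment. The objective on new invasive ventilation would have no section of its own.

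The category 4 sentence stands immediately before the event rule in both sections. It leaves room for the ventilation outcomes to be run in category 4 alone. In 8.2.6 the event rule also reaches beyond the score that defines non-invasive days.

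New ventilation is a clinically important secondary outcome. SAP version 3.0 was written after the interim results had been seen and disclosed (SAP 2.1), so denominators and event rules should not be left for the analyst to settle.

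**Working it through.** The disputed sections state no rate, sample size or power, so there is no planned figure to reproduce. The check compares the text of the sections.

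**1. Inputs.** On the SAP 3.2 scale, 4 is hospitalized without oxygen but needing care, 5 is supplemental oxygen, 6 is non-invasive ventilation or high-flow oxygen, 7 is invasive ventilation or ECMO, and 8 is death.

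| SAP section | Outcome named | Population for that outcome | Further sentence | Event |
|---|---|---|---|---|
| 8.2.4 | new oxygen use | 4 | none | score ≥ 5 |
| 8.2.6 | new non-invasive/high-flow | 4 or 5 | new oxygen use, category 4 | score ≥ 6 |
| 8.2.8 | new non-invasive/high-flow | 4, 5 or 6 | new oxygen use, category 4 | score = 7 |

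**2. Which outcome does 8.2.8 describe?** Read as new non-invasive support, it fails twice. Category 6 is not at risk of starting what it already has, and score 7 is not the non-invasive score. Read as new invasive ventilation/ECMO, it is coherent. Categories 4 to 6 are the baseline categories not yet on invasive support, and score 7 is the score used in 3.3.7. The section also follows 8.2.7 (days of invasive ventilation), and the shell for Table 45 is titled for ventilation/ECMO. The SAP contents list repeats the duplicate heading, so this is not a fault of text extraction.

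**3. The category 4 sentence.** It names new oxygen use, and its population is that of 8.2.4. Taken at face value in 8.2.6 or 8.2.8, it pairs new oxygen use with an event of ≥ 6 or 7, against ≥ 5 in 8.2.4. Taken instead as governing the ventilation outcome, it reduces 4/5 to 4 in 8.2.6 and 4/5/6 to 4 in 8.2.8.

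**4. Incidence against duration in 8.2.6.** For a subject enrolled in category 4 or 5, leaving aside any imputation for death and any days reported after discharge:

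| Worst-of-day scores after enrollment | New use under 8.2.6 (≥ 6) | In-hospital non-invasive days under 3.3.6 (score 6) |
|---|---|---|
| includes 6 | yes | at least 1 |
| includes 7, never 6 | yes | 0 |
| 8, with no 6 or 7 | yes | 0 |

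Table 43 follows the format of Table 41, which sets new-use incidence and days side by side. The two entries can therefore describe different events.

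**5. Would score 6 alone cure this?** No. Protocol 8.1.2.2 and SAP 4.3 record the worst status of each calendar day. A subject who starts non-invasive support and is intubated the same day is scored 7 and may never show a 6. Score 6 alone would miss that genuine new use.

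**6. Size.** The documents give neither baseline category counts nor event risks, so no size can be derived. The following illustration, for the category 4 reading of 8.2.8 only, uses assumed figures. With counts n and score-7 risks v by baseline category,

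rate in categories 4–6 = (n4·v4 + n5·v5 + n6·v6) / (n4 + n5 + n6); rate in category 4 alone = v4.

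Assume 60/200/90 subjects per arm and risks of 3%, 10% and 25%: (1.8 + 20 + 22.5)/350 = 44.3/350 = 12.7%, against 3%. Adding the assumed mixes 100/150/90 and 40/250/150, and a second risk set of 8%, 15% and 40%, gives 12–23% for categories 4–6 against 3–8% for category 4. The denominators are 340–440 against 40–100. The gap follows from the assumed lower risk in category 4. It shows only that the choice of population can matter.

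**The case against.** The strongest reply is that the intended analysis can be recovered. Objective 3.1, the day definition in 3.3.7, the position after 8.2.7 and the title of Table 45 all point to new invasive ventilation. Table 41, the model for Table 45, has a block for subjects not on the support at baseline, which by analogy means categories 4 to 6. An analyst who uses 4/5/6 and score 7 obtains the right invasive rate under a wrong label in the SAP text. This stands, and it limits the consequence. It does not remove the defect, because that analyst has to override the heading, the opening sentence and one population sentence.

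A reader might infer that each section states two rival populations for the same outcome, so that the ventilation rates will be computed in the wrong subjects. The documents do not support that. The category 4 sentence has its own subject, new oxygen use, and displaces the ventilation population only if it is read as governing an outcome it does not name. A reader might also infer that the invasive ventilation objective has been dropped. It lacks a correctly named section, but Table 45 remains to report it.

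For 8.2.6, a threshold of 6 or higher is a defensible escalation outcome, and 8.2.5 also groups categories 6 and 7. That stands for scores 6 and 7, with a label that says so. It does not justify counting a death with no recorded support as new non-invasive use.

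**Conclusion.** The point holds as a fault in operative analysis text. SAP 8.2.8 names one outcome and specifies another. Both sections carry a misplaced sentence that conflicts with 8.2.4. The event rule in 8.2.6 takes in subjects whose only qualifying score is 7 or 8, which 3.3.6 does not count as non-invasive days.

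The size is unknown. Any percentage for lost denominator or for direct progression to score 7 would be an assumption, and the loss to category 4 arises only on a reading that the sentence's own wording does not require. The affected outcomes are secondary summaries without multiplicity adjustment (SAP 6.8). The primary and key secondary analyses are unaffected. The conclusion rests on the SAP text alone and needs none of the illustrative figures.

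**What to change.** 1. Retitle and reword 8.2.8 as incidence and duration of new invasive mechanical ventilation/ECMO, in subjects in category 4, 5 or 6 at enrollment, with the event being a post-enrollment score of 7. This matches Table 45.
2. Delete the sentences on new oxygen use in category 4 from 8.2.6 and 8.2.8, leaving that outcome to 8.2.4.
3. In 8.2.6, keep categories 4 or 5. Name the outcome new non-invasive ventilation/high-flow oxygen or higher support, defined by a score of 6 or 7. Report separately the subjects who score 7 but never 6. Do not count score 8 alone as new use; report such deaths separately. Do not replace the rule with score 6 alone.
4. The threshold of at least 5 in 8.2.4 also admits score 8, so state there how deaths are to count.

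The cost is SAP wording and a few added rows or footnotes in the Table 43 shell. The daily scores are already collected, and no design quantity changes.
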